1.2 Secondary Objectives

1. To assess whether applying the proposed method during percutaneous ablation improves local tumor progression-free survival (LTPFS) rates;
2. Evaluate impact of software use on procedure workflow;
3. Impact of software use on complication rates, quality of life, liver function;
4. Evaluate oncological outcomes (intra-hepatic and overall progression-free survivals, and overall survival)

BACKGROUND

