1.8 Method

RayStation® is a flexible, innovative treatment planning system. It combines unique features like unmatched adaptive therapy capabilities, multi-criteria optimization,

optimization for HDR brachytherapy and external beam therapy with photons, electrons, protons as well as helium and carbon ions. RayStation supports a wide range of treatment machines, providing one control center to create biomechanical deformable registrations using “Morpheus”. Morpheus lets the investigators focus all their skill and experience on evaluating and refining plan quality.

To investigate the impact of the proposed biomechanical model on clinical decisions during ablation guidance and end-point assessment, patients will be randomized in two treatment arms (i.e. experimental arm - including anatomical modeling of the liver, and control arm) with a 1:1 ratio. The primary objective is to assess whether applying biomechanical models during percutaneous ablation will increase the minimal ablation margins, which will be evaluated at the end of the procedure with the proposed software on both cohorts. Additionally, two other distinct end-points will be analyzed: ability of the model to provide tumor identification for ablation probe placement on intra-procedural non-contrast enhanced CT, and local tumor control rates achieved with the clinical application of this model. Operating physicians will be informed in respect which arm the patient was randomized at the time of ablation (figure 3).

[figure not shown]

Figure 3: Patient randomization flowchart

A. Impact on tumor targeting

The clinical trial will be designed according to the optimized parameters from our retrospective analysis. The optimized biomechanical models will be used to assess the accuracy (e.g. the ability of the model to accurately describe the motion, deformation, and volume change and tumor location in the liver between the pre-ablation contrast-enhanced CT and the intra-procedural non-contrast enhanced CT) in both cohort of patients. For the control arm, no information in respect tumor location and targeting will be provided for the operating physician during ablation. Imaging processing using the biomechanical model will be performed after procedure completion. For the experimental

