Figure 4: Image fusion of pre- and post-ablation contrast-enhanced CT using the proposed biomechanical model-based deformable image registration (Morfeus). Blue line: deep learning-based segmentation of the liver; Red line: gross-tumor volume (GTV) contouring; Green line: gross-ablation volume. A minimal ablation margin of < 5 mm was detected on the latero-posterior aspect of the GTV (arrow).

need for re-ablation between the two cohorts will be analyzed to identify the impact of this model on intra-procedural decision-making.

C. Impact on local tumor control

Rates of local recurrence following ablation in the most recent series varies from 20% to 45%. Although re-ablation on a different session is a feasible option in a minority of patients with recurrence at the ablated tumors, this incurs several disadvantages associated with the need to undergo another invasive procedure such as emotional stress, increased exposure to complications related to anesthesia and ablation procedure, radiation exposure, additional use of intravenous contrast media, and

increased associated costs. Given the complex volumetric and spatial changes of the liver post-ablation, the ability to map the previous treatment onto the new treatment plan is critical not only to avoid treatment related toxicities, but also to ensure that the patients receive adequate treatment with optimal coverage. We hypothesize that the use of this current model might improve local tumor control rates at 2-years follow-up. The completion of this aim will evaluate our hypothesis that the applied biomechanical model will improve local tumor control at 2-year when compared to the standard of care control arm.

Note: Final Analysis (n = 100 evaluable subjects)

Figure 5: Clinical Trial schema

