As a secondary objective, the Kaplan-Meier method will be used to estimate local tumor progression-free survival (LTPFS) and 95% confidence intervals for the quantiles of the LTPFS function based on the method of Brookmeyer and Crowley will be calculate for each arm. Time point probabilities (e.g., 2-year LTPFS) and the associated log-log transformed pointwise 95% confidence will also be reported. A multivariate Cox-proportional hazards model will be fitted to the data with ablative margin as a continuous variable to assess the significance of study arm and ablative margin size on LTPFS while simultaneously adjusting for known covariates that effect LTPFS. LTPFS will be measured from date of ablation to earliest date of progression at the ablated lesion, death. Those progression free and alive will be censored at their date of last clinic visit. Similar analysis will be used for 2-years intra-hepatic (progression at any site of the liver) progression-free survival and overall survival. Standard summary statistics will be computed for complication rates, quality of life, and liver function and compared between arms. Statistical significance will be defined as $p < 0.05$.

B. Randomization

A dynamic randomization method by Pocock and Simon will be used with a minimization probability parameter of 0.90. The randomization process will be controlled to ensure a balanced stratification by treatment arm for the factors listed above. Patients will be randomized to either experimental arm or no control arm using the Clinical Trial Conduct (CTC) website (<https://biostatistics.mdanderson.org/ClinicalTrialConduct>), which is housed on a secure server at MDACC and maintained by the MDACC Department of Biostatistics. Access to the website will be gained through usernames and passwords provided by the MDACC Department of Biostatistics to the clinical team. Training on the use of the CTC website to randomize patients on the study will be provided by the biostatistical collaborators. This is an open-label trial with stratified randomization. When a patient is enrolled on the study, the research nurse or coordinator of the study will enter patient's information including medical record number and stratification factors. Through the web interface, after the randomization button is clicked, the result of the randomization will be displayed on the screen for users to view. All data on randomization will be stored in a secure SQL server database.

PROTOCOL MONITORING PLAN

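### The 2-year local-control question has only LTPFS, a composite with death, as its analysis; keep LTPFS and add a supportive analysis of local progression itself

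*Combined protocol and SAP*

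**What the plan says.** Three places bear on the local outcome.

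- **The question.** Section 1.8 lists "local tumor control rates achieved with the clinical application of this model" among the end-points to be analysed. Part C of that section (Impact on local tumor control) states the hypothesis that "the applied biomechanical model will improve local tumor control at 2-year when compared to the standard of care control arm", and motivates it with local recurrence of 20% to 45% in recent series.
- **The declared objective.** Section 1.2 asks whether the method "improves local tumor progression-free survival (LTPFS) rates". The Statistical Design paragraph repeats this as 2-year LTPFS at the ablated lesions.
- **The analysis.** Under Statistical Methods, A. Analysis Plan, LTPFS runs from the ablation to the "earliest date of progression at the ablated lesion, death". Further, "Those progression free and alive will be censored at their date of last clinic visit". Kaplan-Meier curves, 2-year LTPFS by arm and a multivariable Cox model use this endpoint; the Cox model is "to assess the significance of study arm and ablative margin size on LTPFS".

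The other time-to-event outcomes are progression-free survival (intra-hepatic and overall) and overall survival. No section gives time to local progression, a cause-specific model, or a cumulative incidence with death as a competing event.

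**The concern.** The software acts on the margin around the treated tumour, and local control asks whether that tumour regrows. LTPFS asks whether the patient is alive without regrowth. A patient who dies with the ablated lesion still controlled is a failure for LTPFS but not for local control. That all causes of death count is inferred from the unqualified word death in the event definition.

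If such deaths are about equally frequent in the two arms, they add events that carry no information on the software's local effect. The LTPFS hazard ratio then moves toward 1. The margin coefficient in the Cox model is affected in the same way if margin has little bearing on death. At stake is how the section 1.8 hypothesis is read: a modest LTPFS difference could hide a real difference in local control, and no planned result would show it.

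**Working it through.** **The plan's own figure.** The only stated power is for the primary endpoint: 50 per arm, difference 1.132 mm, SD 2, two-sided 0.05. The noncentrality is 1.132 / (2 × √(2/50)) = 2.83. With 98 degrees of freedom the exact t-test power is 80.0%, so the figure reproduces. No power, event count or death rate is given for LTPFS or local control.

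**Inputs.**

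- 50 evaluable per arm, 1:1, at least 2 years of follow-up: from the document.
- Control 2-year local risk of 30%, varied over 20–45%. The range is the one in section 1.8, which gives no time point; using it as a 2-year risk is an assumption.
- Local hazard ratio of 0.5: assumed.
- 2-year death risk of 20%, varied over 5–30%: assumed. Death hazard equal in the two arms: assumed, then relaxed.

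**Formulas.** Exponential hazards over 2 years without loss to follow-up:

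- λ = −ln(1 − risk) / 2
- LTPFS HR = (0.5 λ_L + λ_D) / (λ_L + λ_D)
- power = Φ(|ln HR| × √(events/4) − 1.96)

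**Illustrative case.** λ_L = −ln(0.70)/2 = 0.1783 in the control arm and 0.0892 in the experimental arm. λ_D = −ln(0.80)/2 = 0.1116 in both.

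- LTPFS HR = (0.0892 + 0.1116) / (0.1783 + 0.1116) = 0.69.
- Control arm: 50 × (1 − 0.70 × 0.80) = 22.0 first events, of which 13.5 local and 8.5 deaths.
- Experimental arm: 16.5 first events, of which 7.3 local and 9.2 deaths.
- Together: 20.9 local events and 17.7 deaths, 38.5 in all, so 46% are deaths.
- LTPFS: 0.368 × √(38.5/4) − 1.96 = −0.82, power 21%.
- Cause-specific: 0.693 × √(20.9/4) − 1.96 = −0.38, power 35%.

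**Range (local HR 0.5, same death hazard in both arms).**

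| Local risk | Death risk | LTPFS HR | Deaths among events | Power, LTPFS | Power, cause-specific |
|---|---|---|---|---|---|
| 20% | 10% | 0.66 | 39% | 17% | 26% |
| 20% | 30% | 0.81 | 68% | 10% | 24% |
| 30% | 5% | 0.56 | 16% | 32% | 38% |
| 30% | 20% | 0.69 | 46% | 21% | 35% |
| 45% | 10% | 0.57 | 19% | 43% | 52% |
| 45% | 30% | 0.69 | 45% | 28% | 48% |

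Log-rank simulation of five settings at local HR 0.5 (5,000 runs each) agreed with the formula within 2 points.

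**If the software also affects death.** In the illustrative case, a death hazard ratio of 0.80 gives 31% for LTPFS against 36%; 0.75 gives 35% against 36%; 0.70 gives 38% against 36%. Over local risks of 20–45% and death risks of 10–30%, the two analyses break even at a death hazard ratio of 0.71–0.77.

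**What the added analysis cannot do.** At a hazard ratio of 0.5, 80% power needs 4 × (1.96 + 0.84)² / (ln 0.5)² = 66 events. For death risks of 10–30%, about 13 to 34 local events are expected.

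**The case against.** The strongest reply is that the plan is consistent where it counts. The formal secondary objective is LTPFS, the Statistical Design paragraph names LTPFS, and the analysis uses an event definition that fits the name. Local tumour control appears in the descriptive design section. This stands: a reader might infer that LTPFS is the wrong endpoint or contradicts the objectives, and the documents do not support that. What remains is narrower. Section 1.8 lists local control as an end-point and attaches a 2-year hypothesis to it, and nothing planned estimates it.

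The second reply is that the dilution is conditional. No passage says that deaths are unrelated to the ablation, and section 1.4 argues that aggressive local treatment can prolong survival. This stands too. A reader might take dilution and lost power as certain; they are not, and a sufficiently large effect on death would reverse the comparison. The documents state no such effect for this software.

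Third, a reader might suppose that most LTPFS events will be deaths. The 68% figure belongs to one corner of the range (local risk 20%, death risk 30%); the lower end is 19%, and the documents give no death rate.

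Fourth, power is low either way, and the trial claims none for this outcome. That is correct. The case for the addition is an estimate that answers the stated question, not a decisive test. Nor does it rest on comparison with the cited 20–45%, since the planned comparison is with the randomised control arm.

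Last, events could be tabulated by cause at reporting. They could, but the trial is open-label, and an analysis chosen after the data are seen carries less weight than one written down beforehand.

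**Conclusion.** The point holds as a modest gap: section 1.8 poses a local-control question at 2 years, and its only planned analysis is a composite that also counts deaths. LTPFS is legitimate and should remain.

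The size of the effect rests on a death rate, a local hazard ratio and an absence of arm effect on death, none of which is in the documents. Under those assumptions LTPFS attenuates a local hazard ratio of 0.5 to between 0.57 and 0.81, with power of 10–43% against 24–52% for the cause-specific analysis (local risk 20–45%, death risk 10–30%). With few deaths, or a material survival benefit from the software, the loss is small or absent. The primary endpoint and the sample size are unaffected.

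**What to change.** Keep LTPFS as the declared secondary objective. In the Analysis Plan, pre-specify for the section 1.8 hypothesis a supportive secondary analysis consisting of:

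1. the 2-year cumulative incidence of progression at the ablated lesion, by arm, with death before local progression as a competing event, and a 95% confidence interval;
2. a cause-specific Cox model for local progression with arm;
3. a separate cause-specific Cox model with ablation margin. It is kept separate because margin is what the software is meant to change, so an arm coefficient adjusted for margin would not be the overall arm effect.

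State that conclusions about local control rest on these estimates and their intervals, and that they are not powered.

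No new data are needed. CT is scheduled from 45 days to 24 months (section 1.9), local progression is recorded in OnCore (Protocol Monitoring Plan), and deaths are required for overall survival. The cost is a few sentences of SAP text and standard code. The downside is one more unpowered secondary analysis.

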1.6 Inclusion Criteria

1. Patients presenting with ≤ 3 liver tumors (biopsy-proven or documented by imaging) measuring 1 to 5 cm planned to undergo percutaneous thermal ablation with either microwave or radiofrequency ablation. Patients with more than 3 tumors might also be eligible in case other tumors can be treated with another curative-intended loco-regional therapy (i.e. surgical resection, radiation therapy).
2. Ability to completely cover the target tumor with at least a 5 mm ablation margin.
3. Written informed consent to voluntarily participate in the study and follow-up CT scan schedule
4. Age > 18 years-old
5. Performance status 0-2 (Eastern Cooperative Oncology Group Classification [ECOG])

6. Target tumor should be visualized on contrast-enhanced CT
7. Adequate glomerular filtration rate

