3. INR > 1.5
4. Patients with uncorrectable coagulopathy.
5. Currently breastfeeding or pregnant (latter confirmed by serum pregnancy test).
6. Physical or psychological condition which would impair study participation.
7. ASA (American Society of Anesthesiologists) score of > 4.
8. Any other loco-regional therapies at the target lesion(s) within 30 days of the ablation procedure.

NUMBER OF PARTICIPANTS

Preliminary retrospective data on the control arm suggest that a minimum ablation margin (MAM) of 2mm (SD 2) is generally achieved when ablation is performed without the use of software guidance. A sample size of 50 evaluable subjects in each group will have 80% power to detect a difference in means of -1.132 (the difference between a control arm mean, of 2 mm and the experimental arm mean of 3.132) assuming that the common

standard deviation is 2 using a two group t-test with a two-sided 0.05 significance level.

Assuming an accrual rate of 35 patients per year, the study accrual duration will be around 3 years, with follow-up for at least 2 years, totaling 5 years for the entire study duration. We will have an interim look for superiority once half the evaluable subjects (n=50) have been enrolled. A Lan-Demets spending function using an Obrien-Flemming boundary will be used for superiority stopping boundaries. We will stop enrollment at the control arm at our interim look if our p-value is less than 0.003. East v6.5 was used for sample size calculation. The next 50 patients would be enrolled on the experimental arm only to allow further development of the proposed biomechanical model on clinical practice, as well allow other interventional radiologists at our Department to utilize it.

We plan to screen 140 subjects and expect approximately 20 subjects to be screen failures. Furthermore, subjects after randomization who drop out due to tumor progression, inability to clearly depict target lesions, and major complications precluding further ablation will be considered inevaluable. To account for an expected 20% inevaluable subjects, we will enroll a total of 120 subjects to ensure 100 evaluable subjects.

STUDY PLAN/DESIGN

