1.9 Collecting Time Points

Visit No.	Visit 1	Visit 2		Visit 3	Visit 4	Visit 5	Visit 6	Visit 7
Visit	Screening	Ablation day		45 days	3 months	6 months	1 year	2 years
Interval Window	Within 30 days ablation	Day 0 = ablation of target lesion		(± 14 days) postablation	3 months (± 1 month) postablation	6 months (± 1 month) postablation	12 months (± 1 month) postablation	24 months (± 3 months) postablation
Study Activity		pre	during	post				
Informed consent	x							
Demographic information	x							
Medical, surgical, radiation history	SOC							
BMI and ECOG performance	SOC	SOC		SOC	SOC	SOC	SOC	SOC
Child-Pugh, ASA scores, BCLC staging	SOC			SOC	SOC	SOC	SOC	SOC
CBC, Coagulation, liver function, renal tests	SOC			SOC	SOC	SOC	SOC	SOC
Alpha-fetoprotein	SOC			SOC	SOC	SOC	SOC	SOC
Carcinoembryonic antigen	SOC			SOC	SOC	SOC	SOC	SOC
Pregnancy test	SOC							
Inclusion/exclusion	x	x	x					
Concomitant medications	SOC	SOC		SOC	SOC	SOC	SOC	SOC
QOL questionnaire	x			x	x	x	x	x
Numeric Pain Rating Scale	SOC			SOC	SOC	SOC	SOC	SOC
CT scan	SOC	SOC	SOC	SOC	SOC	SOC	SOC	SOC
Ablation procedure information								
Liquid biopsy (ctDNA)		SOC		SOC		SOC	SOC	SOC
Physician assessment of software utility				x				
Device user experience				x				
Technical success assessment				SOC				
Technical efficacy assessment				SOC				
Follow-up postablation treatment				SOC	SOC	SOC	SOC	SOC

Legend: SOC: Standard of care (data collected as available per standard of care)

PROCEDURE TO OBTAIN CONSENT

The patients will be approached by either the Interventional Radiology Faculty or Research Staff, including research nurses and research coordinators. The principal investigator or designee who are licensed as physician in the state of Texas will obtain informed consent of participants prior to their procedure. During the consenting process patients will be educated and consented for their research participation in this study.

The study will follow the Office of Research SOP04 – Informed Consent Process.

PATIENT INFORMATION AND CONFIDENTIALITY PLAN

Confidentiality will be maintained throughout the study. An informed consent will be obtained prior to the percutaneous ablation procedure. No identifying information will

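### LTPFS is censored at the last clinic visit rather than the last scan, so it is overstated wherever a scheduled visit goes ahead without its CT

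*Combined protocol and SAP*

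**What the plan says.** The rule is in the combined protocol and SAP, Statistical Methods, A. Analysis Plan. The event is defined as "LTPFS will be measured from date of ablation to earliest date of progression at the ablated lesion, death". For everyone else, "Those progression free and alive will be censored at their date of last clinic visit". The affected summaries include the 2-year figure: "Time point probabilities (e.g., 2-year LTPFS) and the associated log-log transformed pointwise 95% confidence will also be reported". The plan also calls for confidence intervals for the quantiles of the curve and a Cox model, and it applies a similar analysis to intra-hepatic progression-free survival and overall survival.

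Three other places bear on the point.

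- Section 1.9 puts a CT in every visit column ("CT scan SOC SOC SOC SOC SOC SOC SOC SOC"), which covers 45 days and 3, 6, 12 and 24 months. Its legend defines the entry as "SOC: Standard of care (data collected as available per standard of care". The quality-of-life questionnaire, by contrast, carries the study's own mark at every follow-up visit.
- Section 1.6, criterion 3, requires "Written informed consent to voluntarily participate in the study and follow-up CT scan schedule".
- Number of Participants plans about 3 years of accrual "with follow-up for at least 2 years, totaling 5 years for the entire study duration". Section 1.9 lists no visit or CT after 24 months.

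The documents do not say what happens to the LTPFS record when a visit takes place without its CT.

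**The concern.** A clinic visit shows that the patient is alive. It does not show that the ablated lesion is controlled. A patient last scanned at month 12 and seen without a scan at month 24 would count as free of local progression for the whole second year. Such a patient stays in the risk set at month 24 but cannot contribute a progression there, so the Kaplan-Meier curve falls too little.

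LTPFS is the first secondary objective (section 1.2). The 2-year rate is the specific secondary analysis named under Statistical Design, and it carries the local-control hypothesis in section 1.8, part C.

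**Working it through.** **The plan's own figure.** The documents give no sample size, event count or power for LTPFS, so there is nothing to reproduce for this endpoint. The stated 80% power with 50 per arm concerns the ablation margin. It reproduces (80.0%, noncentral t) but does not bear on this point.

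**Inputs.** From the documents: CTs at 1.5, 3, 6, 12 and 24 months (section 1.9), and local recurrence of 20% to 45% (section 1.8, part C). Assumed: those recurrence rates are 2-year rates, hazards are constant, visits fall on schedule, and scans are missed independently of progression. The missed-CT rates and the mortality are also assumptions.

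**Step 1: closed form, no deaths.** Let r be 2-year progression, S12 = √(1 − r), p = 1 − S12 (the risk from month 12 to 24 given freedom from progression at 12), and q the share attending month 24 without a CT.

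- Last-CT censoring: S12 × (1 − p) = 1 − r.
- Last-visit censoring: S12 × (1 − p(1 − q)).
- Overstatement: S12 × p × q.

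For r = 0.20, S12 = 0.8944 and p = 0.1056. With q = 0.2, visit censoring gives 0.8944 × (1 − 0.1056 × 0.8) = 0.819, against 0.800. For r = 0.45, S12 = 0.7416 and p = 0.2584, giving 0.7416 × (1 − 0.2584 × 0.8) = 0.588, against 0.550.

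| q | r = 20%: visit v CT | r = 45%: visit v CT | Overstatement (points) |
|---|---|---|---|
| 0% | 80.0 v 80.0 | 55.0 v 55.0 | 0 |
| 10% | 80.9 v 80.0 | 56.9 v 55.0 | 0.9-1.9 |
| 20% | 81.9 v 80.0 | 58.8 v 55.0 | 1.9-3.8 |
| 30% | 82.8 v 80.0 | 60.8 v 55.0 | 2.8-5.8 |

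**Step 2: adding deaths.** Death is an LTPFS event, so the comparison was repeated by Kaplan-Meier simulation with 15% 2-year mortality and CTs missed at months 12 and 24 only. Progression was dated at the CT that shows it. Each rule was compared with the LTPFS that full imaging would give, for r from 20% to 45%.

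| Missed CTs | Last-visit censoring |
|---|---|
| 10% | +0.8 to +1.7 points |
| 20% | +1.8 to +3.6 points |
| 30% | +2.8 to +5.8 points |

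Over the same scenarios:

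- Last-CT censoring that counts every death is too low by 0.5 to 2.7 points. Deaths after the last CT remain events, while survivors with the same gap have left the risk set.
- If patients who die after a scheduled visit with a missed CT are also censored at their last CT, the remaining error is 0.7 points or less.

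**Step 3: extra visits between scans.** If the unimaged time is a clinic visit between the 12- and 24-month CTs with no later follow-up, the bias at 2 years is about 0, because no progression is dated in that interval.

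**Step 4: after 24 months.** With 5 years in total and about 3 years of accrual, early patients could attend clinic well past month 24 with no protocol CT. This leaves the 2-year estimate alone. It can affect the tail of the curve, any quantile read from the tail, and the late risk sets of the Cox model.

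**The case against.** The strongest reply is that the protocol already links visits to scans: a CT is due at each follow-up visit, and patients consent to that schedule. If it is kept, last visit and last CT coincide and the 2-year bias is zero. The standard-of-care mark covers most follow-up rows, not CT in particular, and it gives no rate of missed scans. All of this stands. It makes the problem conditional, but it does not remove it: consent is not completion, and the censoring rule takes no account of whether the scan was done.

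A reader might infer that LTPFS in this trial is certain to be overstated, or that one arm will be favored because the trial is open-label. The documents support neither. Both arms share one CT schedule, and nothing shows that imaging is missed unequally. If it is missed equally, the rule cannot create a difference between arms where none exists. It could only shrink a real one: at 20% missed CTs, for example, 3.6 − 1.8 = 1.8 points between arms with 45% and 20% progression.

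It would also be wrong to read the whole gap between visit censoring and simple last-CT censoring as the plan's error. Part of that gap is the downward bias of the simple alternative.

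Finally, the bias is modest against sampling error. With 60 per arm and LTPFS near 60%, the standard error is about √(0.6 × 0.4 / 60) = 6.3 points. This is fair, but a systematic error is not averaged out and does not show in the confidence interval.

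**Conclusion.** The point holds in conditional form. The censoring date is not tied to imaging, and where a scheduled visit goes ahead without its CT, the progression part of LTPFS and of intra-hepatic progression-free survival can only be pushed upward. The effect on 2-year LTPFS is nil with complete imaging. It is about 0.8-1.7, 1.8-3.6 and 2.8-5.8 points if 10%, 20% and 30% of the 12- and 24-month CTs are missed. Those rates, the 15% mortality, the constant hazards and the independence of missed scans from progression are assumptions. If scans are missed because patients are doing badly, neither censoring rule fully corrects for it.

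The primary endpoint, the minimal ablation margin, is unaffected, and so is overall survival. This is a matter for the secondary analyses, worth settling before outcomes are analyzed so that the censoring date is not chosen afterwards.

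**What to change.** Amend the Analysis Plan as follows.

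1. For LTPFS and intra-hepatic progression-free survival, censor patients who are alive without progression at the date of the last CT or MR that assessed the liver.
2. Where death follows a scheduled visit whose CT was missed, also censor at the last CT or MR in the main analysis.
3. Report two sensitivity analyses: censoring at the last clinic visit, and counting all deaths as events.
4. For overall survival, keep the date last known alive.
5. Report by arm how many scheduled visits lacked a CT, so that readers can judge whether imaging was unequal.

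The cost is a few sentences in the SAP. No visit or scan is added, since CT is already in the data collection schedule. The downside is slightly shorter recorded follow-up and a few deaths not counted in the main LTPFS analysis, which the second sensitivity analysis covers.

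### No use of the scheduled screening values is specified when quality of life and liver function are compared between arms, which leaves precision unused

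*Combined protocol and SAP*

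**What the plan says.** Section 1.2 lists as a secondary objective the "Impact of software use on complication rates, quality of life, liver function". The only analysis sentence for these outcomes is in Statistical Methods, A. Analysis Plan: "Standard summary statistics will be computed for complication rates, quality of life, and liver function and compared between arms". The sentence after it sets significance at p < 0.05, so a formal comparison seems to be intended.

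The schedule in section 1.9 has a row "QOL questionnaire", marked as a study procedure at screening and at 45 days, 3 months, 6 months, 1 year and 2 years. The row "CBC, Coagulation, liver function, renal tests" covers the same visits, but as standard of care. The legend defines that as "SOC: Standard of care (data collected as available per standard of care".

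The plan does name covariate adjustment elsewhere. Its Cox model for local tumor progression-free survival assesses arm and margin "while simultaneously adjusting for known covariates that effect LTPFS". Nothing comparable is written for quality of life or liver function.

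**The concern.** Patients complete a questionnaire at screening for which the plan states no analytic use, and liver tests are scheduled then too. A patient's later score or laboratory value usually depends in part on where that patient started. Enrolment covers primary and secondary liver tumors and ECOG 0 to 2, so starting values are likely to differ between patients. The minimisation factors are histology, RAS status, lesion size, subcapsular location and multiplicity. None of them balances quality of life or liver function directly.

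These outcomes matter because operators in the experimental arm use the software output to decide on further ablation. Quality of life and liver function help to show whether that has a cost for patients. A needlessly wide interval could miss such a cost and then be read as reassurance. With five follow-up visits, several questionnaire scores and an open-label design, an unspecified method also leaves the choice of score, visit and adjustment until after the data are seen.

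**Working it through.** **1. The plan's own figure.** Number of Participants states: "A sample size of 50 evaluable subjects in each group will have 80% power to detect a difference in means of -1.132", with a common "standard deviation is 2 using a two group t-test with a two-sided 0.05 significance level".
- Normal formula: n per arm = 2 × (1.960 + 0.842)² × (2/1.132)², which is just over 49 and rounds up to 50.
- Exact t-test power is 80.0% at 50 per arm and 79.2% at 49.

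The figure reproduces. It belongs to the margin endpoint; the documents give no power or precision for quality of life or liver function.

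**2. Inputs for this point.** 50 per arm is borrowed from the margin endpoint for illustration. Alpha is 0.05 two-sided. The correlation between screening and follow-up value, rho, is an assumption. Variances at the two times are taken as equal.

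**3. Variance of the arm difference, relative to comparing follow-up values alone.**
- ANCOVA on the screening value: 1 − rho²
- Change scores: 2(1 − rho)
- ANCOVA relative to change scores: (1 − rho²) / [2(1 − rho)] = (1 + rho)/2, a cut of (1 − rho)/2

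**4. Detectable difference.** With follow-up values alone at 50 per arm, 80% power needs a difference of (1.960 + 0.842) × √(2/50) = 0.560 SD. ANCOVA multiplies this by √(1 − rho²). The unadjusted sample of equal precision is 50/(1 − rho²) per arm.

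| Assumed rho | Variance cut vs follow-up only | Variance cut vs change score | Detectable difference, ANCOVA (SD) | Power at 0.560 SD | Equivalent unadjusted n per arm |
|---|---|---|---|---|---|
| 0.2 | 4% | 40% | 0.549 | 81.6% | 52 |
| 0.3 | 9% | 35% | 0.535 | 83.6% | 55 |
| 0.5 | 25% | 25% | 0.485 | 89.9% | 67 |
| 0.7 | 49% | 15% | 0.400 | 97.5% | 98 |

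Against follow-up values alone, confidence intervals would be narrower by 1 − √(1 − rho²), which is about 2%, 5%, 13% and 29%.

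**5. Chance baseline difference.** If baseline is not balanced by design, the standard error of the difference in baseline means at 50 per arm is √(2/50) = 0.20 SD, so its 95% range is about ±0.39 SD. If control enrolment stops at the interim look, the randomised comparison has about 25 per arm. The standard error is then √(2/25) = 0.28 SD and the range about ±0.55 SD.

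**The case against.** The strongest reply is that the plan is silent rather than wrong. A reader might infer that it discards the screening values and compares post-treatment values only. The text does not say that, and change from baseline by visit would fit the sentence equally well. This stands, and the point is limited to what is specified. It does not remove the gain, because ANCOVA is also more precise than change scores for any correlation below 1.

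A reader might also infer that chance baseline differences bias the comparison. They do not. In a randomised trial they are random error, already reflected in the confidence interval. Adjustment removes part of that error; the unadjusted analysis remains valid.

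The size of the gain is uncertain. No correlation is given, it will differ between scores, tests and visits from 45 days to 2 years, and at 0.2 the gain over follow-up values alone is only 4%. The figure of 50 per arm is not secure for these endpoints either, given deaths, withdrawals and the possible halt to control enrolment.

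Nor is adjustment free of complications. Liver tests are collected only as available, so some screening values may be missing. A mixed model relies on data being missing at random in a cancer population followed for 2 years, and deaths need a rule. Testing every score at every visit at p < 0.05 would add multiplicity. These objections shape the fix, and they are the reason for naming one main score and visit.

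Finally, these are unpowered secondary endpoints, and liver function is absent from the list of secondary endpoints under Statistical Design. That limits the weight of the point.

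**Conclusion.** The point holds as a question of precision. The plan specifies no use of the screening values or of the repeated visits, and adjusting for the screening value would be better than the stated comparison on either reading of it. For assumed correlations of 0.2 to 0.7, variance falls by 4% to 49% against follow-up values alone, or by 40% to 15% against change scores. These figures assume equal variances at screening and follow-up and a screening value for every patient analysed. The case is firmest for quality of life, where the questionnaire is a study procedure, and weaker for liver tests.

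The documents do not support calling the planned comparison invalid, or extending the point to the primary result or the sample size. Complication rates share the same sentence but have no baseline value, so the argument does not apply to them.

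**What to change.** Add a short paragraph to the Analysis Plan:
- Compare arms on QLQ-C30 scores, and on liver function tests where a screening value is available, by ANCOVA at a named visit or by a repeated-measures mixed model. Use the screening value as covariate in either case.
- Name the main score and the main visit, and treat the other scores and visits as supportive.
- Report arm differences with 95% intervals.
- State how deaths and missing screening values are handled.
- Keep the summary tables as description.

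This needs no new visits, data or patients. The cost is modest extra analysis and, if the mixed model is chosen, reliance on a missing-at-random assumption. Incomplete standard-of-care liver tests will limit what can be gained there. ANCOVA at one visit is the simpler option and would be enough.
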